5.5 Arithmetic Calculations**Change from baseline**

The arithmetic difference between a post-baseline value and baseline for a given timepoint:

(post-baseline value – baseline value).

Percent change from baseline

The change from baseline divided by baseline value and multiplied by 100:

(change from baseline / baseline) * 100.

If the change from baseline is not equal to zero and the baseline value is zero then percent change from baseline is not defined. If the change from baseline is equal to zero and the baseline value is also zero then percent change from baseline is 100.

Fold change from baseline or ratio from baseline

Fold change from baseline equals the post-baseline value divided by the baseline value. If the change from baseline is not equal to 0 and the baseline value is 0 then fold change is not defined. If the change from baseline is equal to 0 and the baseline value is also 0 then fold change is 1.

5.6 Efficacy Assessments**Hybrid Systemic Lupus Erythematosus Disease Activity Index (hSLEDAI)**

The hSLEDAI is a global index that evaluates disease activity and includes 24 items collecting specific manifestations in 9 organ systems: neurological, musculoskeletal, renal, mucocutaneous, general, heart, respiratory, vascular, and hematological. The maximum score is 105.

The hSLEDAI is identical to the SELENA-SLEDAI score except for the scoring of proteinuria, which uses the SLEDAI-2K definition (proteinuria is scored 4 points if proteinuria > 0.5 grams/24 hours [or equivalent urine protein/creatinine ratio]). The hSLEDAI includes scleritis and episcleritis for visual disturbances assessments and scores arthritis only if > 2 joints manifest signs of inflammation. In the hSLEDAI score, inflammation is strictly defined as the presence of tenderness plus one of the following: swelling, effusion, warmth or erythema. In this study, for hSLEDAI scoring purposes, arthritis is required to involve the small joints of hands and/or wrists.

Additional specifications were added in the protocol to reduce potential false positive scores and improve the instrument's ability to score inflammatory manifestations attributable to the disease activity, as described below.

1. Scleritis and episcleritis will be scored only if stability and SLE-relatedness are confirmed by an ophthalmologist.

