8.3 Handling of Missing and Incomplete Data

Subjects may have missing specific data points for a variety of reasons. In general, data may be missing due to a subject's early withdrawal from study, a missed visit, or non-evaluability of a specific clinical or laboratory measurement at its planned clinical visit.

Additionally, as the study was terminated before the planned completion, subjects may have missed clinical visits including not completing the week 52 visit. For efficacy and PRO outcomes, subjects who terminated early due to sponsor decision will be excluded from analyses of data from visits for which they did not have the opportunity to participate in by the date of study termination decision being communicated to sites, i.e. February 28, 2023. Efficacy data collected after this date will be censored and excluded from analyses for that particular visit.

Unless specified, no imputation will be used. The general procedures outlined below describe what will be done when a data point is missing.

Hybrid SLEDAI

In case of completely missing hSLEDAI assessment (e.g. missed visit) or partially missing (e.g. laboratory measurements not available), the missing post-baseline hSLEDAI items will be imputed using last observation carried forward (LOCF) if the previous analysis visit is not missing. Baseline hSLEDAI will not be carried forward to post-baseline.

The hSLEDAI total score will then be computed based on the non-missing and imputed data. **If the hSLEDAI total score cannot be evaluated after imputation, the hSLEDAI score \geq 4 points reduction from baseline will be considered not met.**

CLASI

In case of completely missing CLASI assessment (e.g. missed visit) or partially missing, the missing post-baseline CLASI items will be imputed using LOCF if the previous analysis visit is not missing. Baseline CLASI will not be carried forward to post-baseline.

The CLASI activity score will then be computed based on the non-missing and imputed data. If the CLASI activity score cannot be evaluated after imputation, the CLASI activity score \geq 50% improvement endpoint will be considered not met.

BILAG

In case of completely missing BILAG assessment (e.g. missed visit), the missing post baseline BILAG item scores will be imputed using LOCF if the previous analysis visit is not missing.

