That is, the values of 11.20 and 8.96 will be used in calculating the % reductions in total joint counts, not the values of 10 and 8. Similar proration will be conducted for hands and wrists joint count.

If the tender and swollen joint counts cannot be evaluated after proration, the tender and swollen joint count $\geq 50\%$ improvement from baseline endpoint will be considered not met.

Dates

Missing and incomplete dates will be imputed as outlined in [Appendix E](#).

Laboratory Toxicity Grading

In cases when supplemental information for laboratory toxicity grading is missing or the result is ambiguous, the worse toxicity grade possible will be assigned.

Laboratory Measurements

Laboratory measurements that are below the lower quantification limits will be considered equal to the lower limit of quantification for all analyses unless explicitly noted otherwise.

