9.1 General Considerations

All categorical variables will be summarized using the number and percent of subjects falling into each category and all continuous variables will be summarized using mean,

standard error (SE) or standard deviation (SD), median, first quartile (Q1), third quartile (Q3), minimum, maximum, and number of subjects with observations. Safety endpoints will be summarized descriptively, including the treatment-emergent adverse events and serious adverse events, clinically significant changes in laboratory values and vital signs, and incidence of [REDACTED]. All safety analyses will be performed using the Safety Analysis Set based on subject's actual treatment received.

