9.6.2 Laboratory Test Results

Selected clinical laboratory test results, change and percent change from baseline will be summarized over time by treatment arm. In addition, shift tables from baseline to the worst on-study laboratory toxicity based on the CTCAE version 5, will be presented.

Table 9-4 Selected Safety Laboratory Tests

Chemistry	Hematology	Urinalysis
Creatinine	RBC	Protein/creatinine ratio
Total bilirubin	Hemoglobin	WBC
AST (SGOT)	Hematocrit	RBC
ALT (SGPT)	MCV	
C-reactive Protein	Reticulocytes	Platelets
	WBC	
	Differential	
	
 • Eosinophils • Basophils • Lymphocytes 	

ALT = alanine aminotransferase; AST = aspartate aminotransferase; MCV = mean corpuscular volume; RBC = red blood cell count; SGOT = serum glutamic-oxaloacetic transaminase; SGPT = serum glutamic-pyruvic transaminase; WBC = white blood cell count

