Appendix D. Analytical Windows

The last measurement for the endpoint of interest taken prior to or on the first dose of IP in this study, unless stated otherwise, will be defined as a baseline visit and the analysis visit name will be 'Baseline'. For any visit up to Day 1 pre-dose which is not a baseline visit, the analysis visit will be 'Pre-analysis'.

Since the actual visit for a subject may not exactly coincide with their scheduled visit date, to allow for variations in scheduling, the following visit windows will be used to assign evaluations to a most appropriate nominal visit for analysis and summarization. Furthermore, there will be no gaps between visit windows in order to include as many data points as possible for summarization.

If more than one actual visit (including the unscheduled visits) falls within the same defined window, the visit closest to the target day with non-missing data will be considered for analysis. If two actual visit dates are at the same distance from the target day, the latest visit with non-missing data will be considered for analysis.

The rules above for selecting a visit from multiple ones within the same visit window are not applicable to retest values of lab data. If the lab measurement is a retest, the retest value will be used.

Efficacy assessment (tender/swollen joint count, hSLEDAI, BILAG, SELENA-

SLEDAI Flare Index, PGA, CLASI), weight, and laboratory assessment [REDACTED]

[REDACTED], chemistry, urinalysis)

Study Visit	Target Day	Study Day
Baseline	1	Last evaluation prior to or on Study Day 1
Week 4	29	2 - 42
Week 8	57	43 - 70
Week 12	85	71 - 98
Week 16	113	99 - 126
Week 20	141	127 - 154
Week 24	169	155 - 182
Week 28	197	183 - 210
Week 32	225	211 - 238
Week 36	253	239 - 266
Week 40	281	267 - 294
Week 44	309	295 - 322
Week 48	337	323 - 350
Week 52	365	351 - 394

Hematology

Study Visit	Target Day	Study Day
Baseline	1	Last evaluation prior to or on Study Day 1
Week 4	29	2 - 42
Week 8	57	43 - 70
Week 12	85	71 - 98
Week 16	113	99 - 126
Week 20	141	127 - 154

Week 24	169	155 - 182
Week 28	197	183 - 210
Week 32	225	211 - 238
Week 36	253	239 - 266
Week 40	281	267 - 294
Week 44	309	295 - 322
Week 48	337	323 - 350
Week 52	365	351 - 392
Week 60	421	393 - 448
Week 68	477	≥ 449

Vital sign

Study Visit	Target Day	Study Day
Baseline	1	Last evaluation prior to or on Study Day 1
Week 2	15	2 - 21
Week 4	29	22 - 35
Week 6	43	36 - 49
Week 8	57	50 - 63
Week 10	71	64 - 77
Week 12	85	78 - 91
Week 14	99	92 - 105

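### Two minor SAP slips in descriptive tables: no change from a zero baseline is scored as +100%, and one PRO visit-window boundary out of 73 is off the midpoint

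*SAP*

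**What the plan says.** **Percent change.** SAP 5.5 defines percent change as the change divided by baseline, times 100. With a zero baseline and a non-zero change, the result is left undefined. With both at zero, the rule is: "If the change from baseline is equal to zero and the baseline value is also zero then percent change from baseline is 100". The fold-change paragraph directly below treats the same case differently: "If the change from baseline is equal to 0 and the baseline value is also 0 then fold change is 1".

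SAP 9.6.2 uses the quantity: "Selected clinical laboratory test results, change and percent change from baseline will be summarized over time by treatment arm". Table 9-4 includes eosinophils, basophils and urine WBC and RBC. Under SAP 9.1, "all continuous variables will be summarized using mean" together with the quartiles, minimum and maximum, among other statistics.

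**PRO windows.** Appendix D says its windows serve to "assign evaluations to a most appropriate nominal visit for analysis and summarization". When several records share a window, "the visit closest to the target day with non-missing data will be considered for analysis". The PRO table gives week 12 (target day 85) days 57-98, week 24 (target day 169) days 99-210, and week 36 (target day 253) days 211-280.

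**The concern.** A value that stays at zero has not changed, yet the percent-change rule gives it the number that a doubled value would get. The figure 100 makes sense as percent of baseline, not as percent change. The rule is also lopsided. A subject who rises from zero is undefined and drops out of the percent-change summary, while a subject who stays at zero remains in it at +100%. Every zero-baseline record that contributes is therefore a false doubling.

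In the PRO table, the week 12 to week 24 boundary is far from the middle of the gap. A questionnaire completed two weeks after the week 12 target can be reported as week 24, ten weeks before that target.

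At stake are the percent-change laboratory tables and the PRO summaries at weeks 12 and 24, the latter being listed secondary endpoints. SAP section 10 removes treatment comparisons, so these descriptive tables are what will be reported.

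**Working it through.** **1. Zero-to-zero percent change**

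- The SAP 5.5 formula gives 0/0 × 100, which is undefined. A convention is needed, and the stated 100 cannot be derived from the formula.
- Percent change = (fold change − 1) × 100. With the SAP's own fold change of 1 this is (1 − 1) × 100 = 0.
- The value 100 arises only as fold change × 100 = 1 × 100, which is percent of baseline.
- SAP 8.3 on assay limits says: "Laboratory measurements that are below the lower quantification limits will be considered equal to the lower limit of quantification". A test below the limit at both visits therefore gives (LLOQ − LLOQ)/LLOQ × 100 = 0%. This is a different case from a recorded zero, but here too an unchanged low result comes out as 0%.

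If a share q of a test's percent-change values is zero-to-zero, the mean exceeds its value under a score of 0 by 100 × q. The documents do not give q, so the shares below are assumptions.

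| Assumed q | Shift in mean (points) |
|---|---|
| 1% | +1 |
| 5% | +5 |
| 10% | +10 |

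One such record makes the reported maximum at least 100. If all other values are below 100, the third quartile becomes 100 once q exceeds 25%.

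**2. Window boundaries**

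For each pair of consecutive post-baseline windows in Appendix D, the start of the later window was compared with (earlier target + later target)/2. Baseline cut-offs and final upper limits were left out.

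| Table | Boundaries | At midpoint |
|---|---|---|
| Efficacy, weight, laboratory | 12 | 12 |
| Hematology | 14 | 14 |
| Vital signs | 29 | 29 |
| SDI | 1 | 1 |
| PK | 12 | 12 |
| PRO | 5 | 4 |
| Total | 73 | 72 |

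The exception is PRO week 12 to week 24: (85 + 169)/2 = 127, against day 99 in the SAP.

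The width of the gap does not explain it. The other two 84-day gaps are week 24 to week 36 in the PRO and PK tables. Both have midpoint (169 + 253)/2 = 211, and both split at day 211.

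Distances for the affected days (126 − 99 + 1 = 28 days):

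| Day | From day 85 | From day 169 |
|---|---|---|
| 99 | 14 | 70 |
| 126 | 41 | 43 |

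All 28 days are nearer week 12.

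Window widths:

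| Visit | SAP | Split at midpoint |
|---|---|---|
| Week 12 | 57-98: 42 days (28 before target, 13 after) | 57-126: 70 days (28 before, 41 after) |
| Week 24 | 99-210: 112 days (70 before, 41 after) | 127-210: 84 days (42 before, 41 after) |

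With no record nearer day 169, a record on days 99-126 is reported as week 24. If there is one nearer day 169, the earlier record is used at neither visit. Week 12 is then missing if nothing falls on days 57-98, because SAP 8.3 has no PRO imputation rule. A subject with records only on days 100 and 169 is an example.

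**The case against.** **On percent change:** fold change is not used in any visible analysis, so the clash with it is textual. The assay-limit rule covers a different case and reduces the number of exact zeros. Nothing in the SAP shows how often the listed tests are recorded as exact zeros, or whether urine counts are numeric. Absolute values and changes are shown alongside. All of this limits the size. None of it makes +100% a correct description of no change.

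**On the windows:** the SAP states no midpoint rule, and choosing the most appropriate visit is a judgement. On-schedule visits (±3 business days, Protocol 9.1.2) never fall on days 99-126. For PRO outcomes, SAP 8.3 already provides that subjects terminated by the sponsor "will be excluded from analyses of data from visits for which they did not have the opportunity to participate in", judged at 28 February 2023. Appendix D also aims to keep as many data points as possible, and the midpoint split can lose one. Take a subject with an on-schedule week 12 record, a second on day 110 and nothing later. At present both records are used; after the change, the day 110 record is dropped.

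These points stand as limits on reach, and they make the boundary an inconsistency to correct or explain. The lost-record example carries little weight: day 110 is 25 days from week 12 and 59 from week 24, so the record now kept is one carrying the wrong label. The sponsor-termination exclusion does not cover other early withdrawals or unscheduled records.

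**Conclusion.** Both points hold, and both are minor. The zero-to-zero rule is wrong as written and is the stronger of the two. Its size is 100 × q points on the mean of an affected test, with q unknown. It depends on some laboratory results being recorded as exact zeros, which is plausible for basophils, eosinophils and urine cells but not stated. The PRO boundary is an unexplained exception, 28 days earlier than the pattern of the other 72. It affects only off-schedule records on days 99-126, and their number is not in the documents.

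SRI-4, BICLA and LLDAS do not use percent change. The 50% joint and CLASI endpoints require a baseline of at least 6 joints or a score of at least 8, so the zero-baseline rule cannot reach them. The interim futility decision rested on SRI-4 and is untouched.

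**What to change.** - **SAP 5.5:** set percent change to 0, or to not defined, when baseline and change are both zero. Setting it to 0 agrees with the fold change of 1.
- **SAP Appendix D, PRO table:** set week 12 to days 57-126 and week 24 to days 127-210, or state why this one boundary differs from the rest.

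The cost is one sentence and two window limits, plus reprogramming of the two derivations. No new data are needed.

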Subjects will undergo a screening visit to confirm eligibility requirements. Baseline/day 1 visit should not occur prior to confirmation of subject's SLE-related eligibility by the adjudication team and must occur up to 33 days from the screening visit. At baseline/day 1 visit, prior to randomization, the subject must present with disease activity (defined by clinical hSLEDAI score ≥ 4) and stability and compliance with OCS and other immunosuppressant/immunomodulator doses (by reviewing medication history). Subjects may be randomized at any time after confirmation of all eligibility criteria, but the maximum time between initiation of screening and randomization is 33 days. Subjects who do not meet all the eligibility requirements at the baseline/day 1 visit will be considered screen failures. Subjects may be allowed to rescreen as detailed in Section 9.1.1.

After randomization, adjudication reviews will be completed throughout the study period on blinded endpoint data from enrollment to week 52 for all randomized subjects and for all visits. This includes review of all efficacy-related endpoint data.

Immunosuppressant/immunomodulator dose should remain stable through week 52. For OCS, initiation of, or temporary increases in OCS are allowed from weeks 0 to 8, provided that return to baseline dose occur within the subsequent 2 weeks, as outlined in Section 7.1.4.2. OCS can be tapered at the investigator's discretion but shall not be changed during the last 8 weeks (week 44 to 52) of the 52-week treatment period.

Subjects listed below will be allowed to continue the study but will be considered treatment failures for primary efficacy endpoint analyses for the subsequent time points. **These subjects will also be allowed to continue investigational product at the investigator's discretion, except subjects who initiate any immunosuppressant/immunomodulator listed in Section 7.1.7 (treatments a through i).**

- Subjects requiring initiation or increase in OCS dose > 5 mg/day (prednisone or equivalent), **or intramuscular (IM) CS or intravenous (IV) CS** at any time point during the study, subjects requiring initiation or increase in OCS dose ≤ 5 mg/day (prednisone or equivalent) after week 10, or subjects requiring initiation or increase in OCS dose ≤ 5 mg/day (prednisone or equivalent) from week 0 to week 8 who cannot return to their baseline dose within the following 2 weeks (Section 7.1.4.2).

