7.1.4 Other Therapies

7.1.4.1 Immunosuppressants/Immunomodulators

Subjects should receive stable doses of immunomodulators and/or immunosuppressants agents from \geq 8 weeks prior to screening through week 52. If a subject requires a higher dose of an immunosuppressant/immunomodulator or requires a new immunosuppressant/immunomodulator at any time during the study period (other than CS, see below), the subject may continue the study but will be considered treatment **failures for primary efficacy endpoint analyses for the subsequent time points. These subjects will also be allowed to continue investigational product at the investigator's discretion, except subjects who initiate any immunosuppressant/immunomodulator listed in Section 7.1.7 (treatments a through i).**

Subjects may reduce dosage in immunomodulators and/or immunosuppressants if the subject develops unacceptable side effects or abnormal laboratory values attributable to these medications.

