9.2.2.11 Systemic Lupus Erythematosus Responder Index

The SRI-4 will be calculated as detailed in Luijten et al, 2012. **A subject achieves SRI-4 response if all of the following criteria are met:** ≥ 4 -point reduction from baseline in hSLEDAI score, AND no new BILAG **2004** A score and no > 1 new BILAG B domain scores compared with baseline (eg, **no B, C, D, or E scores at baseline becomes A or no more than 1 C, D, or E score at baseline becomes B**), AND no ≥ 0.3 -point deterioration from baseline in PGA VAS score (**scale 0 to 3**), AND **no use of more than protocol-allowed therapies (ie, initiation or increase in OCS dose > 5 mg/day prednisone [or equivalent] or IM CS or IV CS at any time point during the study; initiation or increase in OCS dose ≤ 5 mg/day prednisone [or equivalent] after week 10; initiation or increase in OCS dose ≤ 5 mg/day prednisone [or equivalent] between week 0 and week 8 that was not returned to baseline dose within the following 2 weeks; increase in current or initiation of new immunosuppressant/immunomodulator(s) at any time during the study)**. The latest visit date among hSLEDAI, BILAG, and PGA will be considered the SRI-4

visit date. In the case when all 3 visit dates are missing, the upper limit of the analytic window of this visit will be the SRI-4 visit date. When all 4 criteria are met, the subject is a responder at that time point according to the SRI-4 definition.

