9.2.2.12 BICLA Index Response

The BICLA response is defined as at least 1 gradation of improvement in baseline BILAG domain scores in all body systems with moderate or severe disease activity at entry (eg, all A [severe disease] domain scores falling to B [moderate], C [mild], or D [no activity], and all B domain scores falling to C or D); no new BILAG 2004 A domain score and no > 1 new BILAG 2004 B domain scores compared with baseline; **no worsening of the hSLEDAI score from baseline; no \geq 0.3-point deterioration from baseline in PGA (scale 0 to 3); and no use of more than protocol-allowed therapies (ie, initiation or increase in OCS dose > 5 mg/day prednisone [or equivalent] or IM CS or IV CS at any time point during the study; initiation or increase in OCS dose ≤ 5 mg/day prednisone [or equivalent] after week 10; initiation or increase in OCS dose ≤ 5 mg/day prednisone [or equivalent] between week 0 and week 8 that was not returned to baseline dose within the following 2 weeks; increase in current or initiation of new immunosuppressant/immunomodulator(s) at any time during the study); and no initiation of non-protocol treatment for SLE** (Wallace et al, 2011; Wallace et al, 2014).

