2.1 Objectives and Endpoints/Estimands

Objectives	Endpoints
Primary	

 Evaluate the efficacy of rozibafusp alfa at week 52 as measured by the Systemic Lupus Erythematosus Responder Index (SRI-4) 	
 SRI-4 response at week 52
Primary Estimand	

The primary estimand is the difference in SRI-4 response rates between each rozibafusp alfa dose group and placebo at week 52 for all subjects with SLE with inadequate response to SOC therapy who are randomized, regardless of investigational product (IP) discontinuation; subjects will be considered non-responders for using more than protocol-allowed therapies as follows:
 
 initiation or increase from baseline in oral corticosteroid (OCS) dose > 5 mg/day (prednisone or equivalent) or intravenous (IV) or intramuscular (IM) at any time point during the study initiation or increase from baseline in OCS dose ≤ 5 mg/day (prednisone or equivalent) after week 10 initiation or increase from baseline in OCS dose ≤ 5 mg/day (prednisone or equivalent) between week 0 and week 8 that was not returned to baseline dose within the following 2 weeks initiation or increase from baseline of immunosuppressant/immunomodulator(s) at any time during the study 	
Secondary	

 Evaluate the efficacy of rozibafusp alfa at week 24 	
 SRI-4 response at week 24 British Isles Lupus Assessment Group (BILAG)-based Combined Lupus Assessment (BICLA) response at week 24

 Evaluate the efficacy of rozibafusp alfa at week 52 	
 Lupus Low Disease Activity State (LLDAS) at week 52

Objectives	Endpoints
	
 BICLA response at week 52

 Evaluate the efficacy of rozibafusp alfa as measured by SRI-4 response with oral corticosteroid (OCS)-tapering 	
 SRI-4 response at week 52 with reduction of OCS to \leq 7.5 mg/day by week 44 and sustained through week 52 in subjects with a baseline OCS dose \geq 10 mg/day

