Systemic Lupus Erythematosus Responder Index (SRI-4)

A subject achieves SRI-4 response if all of the following criteria are met:

1. ≥ 4 -point reduction from baseline in hSLEDAI score
2. no new BILAG 2004 A and no > 1 new BILAG 2004 B domain scores compared with baseline (e.g. no B, C, D or E scores at baseline becomes A or no more than 1 C, D or E score at baseline becomes B)
3. and < 0.3 -point deterioration from baseline in PGA (scale 0 to 3).
4. no use of more than protocol-allowed therapies (i.e. initiation or increase from baseline in oral corticosteroid (OCS) dose > 5 mg/day (prednisone or equivalent) or intravenous (IV) or intramuscular (IM) at any time point during the study; initiation or increase in OCS dose ≤ 5 mg/day (prednisone or equivalent) after week 10; initiation or increase in OCS dose ≤ 5 mg/day (prednisone or equivalent) between week 0 and week 8 that was not returned to baseline dose within the following 2 weeks; initiation or increase from baseline of immunosuppressant/immunomodulator(s) at any time during the study.)

The latest visit date among hSLEDAI, BILAG and PGA will be considered the SRI-4 visit date. In the case when all three visit dates are missing, the upper limit of the analytic window of this visit will be the SRI-4 visit date.

BILAG-based Composite Lupus Assessment (BICLA)

A subject achieves BICLA response if all of the following criteria are met:

1. at least one gradation of improvement in baseline BILAG domain scores in all body systems with moderate or severe disease activity at entry (e.g., all A (severe disease) domain scores at baseline falling to B (moderate), C (mild), or D (no activity), and all B domain scores at baseline falling to C or D)
2. no new BILAG 2004 A domain score and no > 1 new BILAG 2004 B domain scores compared with baseline
3. no worsening of the hSLEDAI score from baseline
4. < 0.3-point deterioration from baseline in PGA (scale 0 to 3)

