5. and no use of more than protocol-allowed therapies (i.e. initiation or increase from baseline in oral corticosteroid (OCS) dose > 5 mg/day (prednisone or equivalent) or intravenous (IV) or intramuscular (IM) at any time point during the study; initiation or increase in OCS dose ≤ 5 mg/day (prednisone or equivalent) after week 10; initiation or increase in OCS dose ≤ 5 mg/day (prednisone or equivalent) between week 0 and week 8 that was not returned to baseline dose within the following 2 weeks; initiation **or increase from baseline** of immunosuppressant/immunomodulator(s) at any time during the study.

Swollen and Tender Joint Count

Joints that have been replaced during the study, or have suffered trauma or received intra-articular injections, are considered non-evaluable.

Swollen Joint Count Assessments – A total 28 joints will be scored for presence or absence of swelling. A separated score for joints in the hands and wrists will be calculated.

Tender Joint Count Assessments – A total 28 joints will be scored for presence or absence of tenderness. A separated score for joints in the hands and wrists will be calculated.

Swollen and Tender Joint Count Assessments: joints in hands and wrists will be scored for the simultaneous presence of absence of swelling and tenderness.

Cutaneous Lupus Erythematosus Area and Severity Index (CLASI)

The CLASI consists of 2 scores, the first summarizes the activity of the disease while the second is a measure of the damage done by the disease. Activity is scored based on erythema, scale/hyperkeratosis, mucous membrane involvement, acute hair loss and non-scarring alopecia. Damage is scored in terms of dyspigmentation and scarring, including scarring alopecia. Subjects are asked whether dyspigmentation due to cutaneous lupus lesion usually remains visible for more than 12 months, which is taken to be permanent. If so, the dyspigmentation score is doubled. The scores are calculated by simple addition based on the extent of the symptoms. The CLASI is designed as a table where the rows denote anatomical areas, while the columns score major clinical symptoms. The extent of involvement for each of the skin symptoms is documented according to specific anatomic areas that are scored according to the worst affected lesion within that area for each symptom.

A CLASI response is defined as $\geq 50\%$ improvement of CLASI activity score from baseline.

Lupus Low Disease Activity State (LLDAS)

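### The SAP's excess-therapy criterion for SRI-4 and BICLA is not tied to the visit being scored, so later rescue can cancel an earlier response; its low-dose steroid clauses also differ between SAP 2.1 and 5.6

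*SAP*

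**What the plan says.** **Time frame.** SAP 2.1 (primary estimand) and SAP 5.6 (SRI-4 criterion 4, BICLA criterion 5) treat a subject as a non-responder for OCS started or raised by more than 5 mg/day, IV or IM steroid, or a started or raised immunosuppressant, at any time in the study. The ≤ 5 mg/day clause has a start (after week 10) but no end. In 5.6 the text runs: "IM) at any time point during the study; initiation or increase in OCS dose ≤ 5 mg/day (prednisone or equivalent) after week 10". SAP 5.6 defines an SRI-4 visit date but does not use it in criterion 4, and it gives BICLA no date.

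Protocol 9.2.2.11 and 9.2.2.12 carry the same whole-study wording. However, 9.2.2.11 scores by visit: "When all 4 criteria are met, the subject is a responder at that time point according to the SRI-4 definition". Protocol 5.1 adds that subjects with such therapy "will be considered treatment failures for primary efficacy endpoint analyses for the subsequent time points", and 7.1.4.1 repeats this for immunosuppressants ("failures for primary efficacy endpoint analyses for the subsequent time points"). Protocol 7.1.4.2 calls OCS rescue a failure for the primary endpoint and gives no time limit.

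**Reference dose.** SAP 2.1 has "initiation or increase from baseline in OCS dose ≤ 5 mg/day (prednisone or equivalent) after week 10". SAP 5.6 names baseline in the > 5 mg/day and immunosuppressant clauses, but not in the post-week-10 clause or in "initiation or increase in OCS dose ≤ 5 mg/day (prednisone or equivalent) between week 0 and week 8". The protocol gives no reference dose either: "subjects requiring initiation or increase in OCS dose ≤ 5 mg/day (prednisone or equivalent) after week 10" in 5.1 and "initiation or increase in OCS dose ≤ 5 mg/day prednisone [or equivalent] after week 10" in 9.2.2.12.

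**The concern.** Whether someone responded at week 24 should not depend on what they took at week 40. Under the SAP wording it can. The data needed for this will exist, because protocol 7.8.2 collects concomitant therapy to the end of safety follow-up. Sponsor termination also took subjects off drug and followed them for 16 weeks (SAP 3.1), a period in which rescue is plausible. SAP 8.3 cuts off efficacy data after 28 February 2023 but says nothing about medication events after that date. SAP 5.3 sets each subject's end of study at the CRF date, so follow-up falls inside the study.

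Counts and percentages of responders by arm are the whole primary summary (SAP Table 9-1). The definition of a responder therefore carries all the weight. The reference-dose mismatch adds a second, smaller uncertainty. It matters most for BICLA, which SAP 2.1 does not cover.

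**Working it through.** The plan gives no figure to reproduce. The check compares the passages and scores hypothetical dose histories under each reading.

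**1. The passages side by side**

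| Place | When excess therapy counts | Reference dose for a ≤ 5 mg/day increase |
|---|---|---|
| SAP 2.1 | Whole study; no end date | Baseline |
| SAP 5.6, SRI-4 and BICLA | Whole study; no end date | Not stated |
| Protocol 9.2.2.11, 9.2.2.12 | Whole study; 9.2.2.11 scores by visit | Not stated |
| Protocol 5.1 | Later time points only (primary endpoint) | Not stated |
| Protocol 7.1.4.1 | Later time points only (primary endpoint) | Not applicable |
| Protocol 7.1.4.2 | No limit given (primary endpoint) | Not stated |

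The SAP does tie medication to the visit elsewhere: both LLDAS drug criteria in Appendix B are judged at the visit.

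**2. How far forward the literal rule reaches.** The last dose is at week 50 and follow-up lasts at least 16 weeks: 50 + 16 = week 66. From week 24 that is 66 − 24 = 42 weeks. From week 52 it is 66 − 52 = 14 weeks.

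**3. Effect of the time limit.** Hypothetical subjects, baseline 10 mg/day, increases measured from baseline:

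| OCS history | Week 24, events up to visit | Week 24, whole study | Week 52, events up to visit | Week 52, whole study |
|---|---|---|---|---|
| 12.5 at week 30 | not a failure | failure | failure | failure |
| 20 at week 30 | not a failure | failure | failure | failure |
| 12.5 at week 56 | not a failure | failure | not a failure | failure |

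The time limit mainly moves week-24 status. It moves week 52 only for rescue after week 52.

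**4. Effect of the reference dose.** Again with baseline 10 mg/day, tapered to 5 at week 20:
- Up to 7.5 at week 30: 7.5 − 10 = −2.5 from baseline, 7.5 − 5 = +2.5 from the current dose.
- Up to 10 at week 30: 0 from baseline, +5 from the current dose.

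At week 52 neither is a failure against baseline. Both would be failures against the current dose.

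The current-dose reading can be tested for coherence. Take baseline 20, tapered to 10, after week 10:
- Up to 12.5: +2.5 from current, so it fails the ≤ 5 mg/day clause.
- Up to 18: +8 from current, so it is outside the ≤ 5 mg/day clause. The > 5 mg/day clause is measured from baseline: 18 − 20 = −2, so it does not fail there either.

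The smaller rise fails and the larger one passes. That makes baseline the sensible reading.

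**5. Weeks 8 to 10.** Protocol 7.1.4.2 allows a ≤ 5 mg/day start or increase begun in weeks 0 to 8. The failure clauses cover weeks 0 to 8 without return to baseline, and after week 10. With the SAP Appendix D target days (week 8 = day 57, week 10 = day 71), 71 − 57 = 14 days are neither allowed nor a failure.

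**6. Scale.** The documents give no frequency for these histories. At week 24, 25% of the 200 subjects planned for the sixth interim analysis is about 50 on placebo, so one reclassified placebo subject is 1/50 = 2.0 points. Subjects who reached week 24 later would make it less. The week-52 and taper-subset denominators are not given.

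**The case against.** The best defence is that the protocol already supplies the limit. Sections 5.1 and 7.1.4.1 make failure run forward, 9.2.2.11 scores each visit on its own, and the SAP says that it details the protocol's analyses. The stability requirements for OCS and immunosuppressants run only to week 52, so revoking a week-52 response for treatment at week 66 is a strained reading. The SRI-4 visit date was presumably defined for comparison with medication dates. Protocol 7.1.4.2 need not conflict, since the primary endpoint is a single time point. Much of this stands. What remains is that the forward rule is worded for the primary endpoint only, the SAP does not restate it, and week-24 SRI-4 and BICLA at both visits have no stated limit.

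The summary of Amendment 3 says that the Important Protocol Deviation list is now used to define excess therapy. That list is not in the documents and may settle dates and reference dose. SAP 9.3 uses it only for a table and a subject list, so this cannot be relied on, but it does lower confidence that programmers would diverge.

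On reference dose, a reader might infer that SAP 2.1 and 5.6 are two competing rules. The documents do not support that. The other clauses of the same sentence name baseline, the weeks 0 to 8 clause requires return to the baseline dose, and the current-dose reading is incoherent (step 4). The one pull the other way is that the SELENA-SLEDAI flare criteria in 5.6 compare prednisone with the previous assessment.

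**Conclusion.** The main point holds: as written, the SAP criterion lets later rescue, including rescue in the 16-week off-drug follow-up, turn a week-24 or week-52 response into a non-response. The protocol's forward-only rule contradicts this for the primary endpoint and is silent for the rest. The reference-dose difference is a matter of making two sections match. The weeks 8 to 10 gap is secondary and is shared by protocol and SAP.

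The size is unknown. The effect is on reported proportions only, because SAP section 10 removes all treatment comparisons; no test depends on it.

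A reader might also infer that the OCS-taper endpoint is especially exposed, because any re-increase compatible with it stays 10 − 7.5 = 2.5 mg/day below baseline and so could never fail under SAP 2.1. That holds only for the dose kept from week 44. The endpoint sets no cap before then: baseline 10, taper to 8, 12.5 at week 20 and 7.5 by week 44 meets the dose condition, yet is above baseline after week 10.

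Severity is minor to should-fix, with moderate confidence.

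**What to change.** Before the final lock:

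- **Date rule.** In SAP 2.1 and 5.6, count only events dated on or before the SRI-4 visit date, at every scored visit. Give BICLA an equivalent date; it uses the same three instruments. Appendix E already handles partial start dates.
- **One definition.** Use identical failure wording in SAP 2.1, SRI-4 criterion 4 and BICLA criterion 5. The sponsor should confirm the reference dose for every OCS clause and record any departure from the protocol in SAP section 10.
- **Weeks 8 to 10.** The sponsor should reconcile protocol 5.1, 7.1.4.2, 9.2.2.11 and 9.2.2.12 with SAP 2.1 and 5.6. Which clinical rule applies is the sponsor's decision.

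The first two cost a few lines of SAP text and a programming check, with no new data. The third needs a recorded sponsor decision, because SAP wording alone cannot settle the protocol passages.
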